3.2 Rationale for Study Design

This is a Phase 1 first-time-in-human study designed to evaluate the safety, reactogenicity, and immunogenicity of the GSK-CureVac second-generation CV2CoV vaccine to prevent COVID-19 disease caused by existing and new emerging strains of the SARS-CoV-2 virus. This study will evaluate the CV2CoV vaccine in a booster vaccination setting. The study comprises an adult population of participants who have received a documented full primary vaccination series (2 doses only) with a licensed or authorized mRNA COVID-19 vaccine (only Moderna or Pfizer vaccines). The second-generation vaccines are based on the firstgeneration CVnCoV vaccine, for which efficacy and safety data have been collected in the ongoing Phase 2b/3 study (NCT04652102). The rationale for evaluation of doses from 2 to 20 µg is based on the following: 1) The data from this study will support decisions as to whether the candidate vaccine should be further evaluated in advanced phase clinical trials. 2) The data from this study will guide dose selection. 3) The proposed study will support development of the platform. Specifically, if the CV2CoV monovalent candidate induces robust immune responses with an acceptable safety profile, there may be potential to develop future multivalent vaccines to prevent COVID-19 disease based on this platform. The rationale for including older adults in this study is because this age group is at increased risk for severe COVID-19. In addition, the efficacy of the CVnCoV vaccine was lower in older adults than in younger adults < 65 years of age. Thus, safety and immunogenicity data on CV2CoV in this age group will be critical to guiding decisions on whether the CV2CoV vaccine candidate should be advanced further in development.

The starting doses of the CV2CoV vaccine are 2 μ g and 4 μ g in Cohort 1. These starting doses are based on previously tested doses for the first-generation CVnCoV vaccine.

The maximum planned dose of the CV2CoV vaccine is 20 µg in the present study. In the Phase 1 study, the reactogenicity profile of the first-generation CVnCoV vaccine was dose-dependent from 2 µg to 20 µg. Solicited reactions were more commonly systemic with a frequency of reports generally similar after the administration of the first and the second dose (except for 8 µg and 16 µg). The severity of systemic solicited events increased with dosages with an overall rate of of participants reporting a Grade 3 event. However, Grade 3 solicited events were mostly short-lived and self-limiting, eg, Grade 3 AEs only lasted for 1 day and, 1 participant reported a Grade 3 myalgia after the second dose for 3 consecutive days and resolved on the fourth day. Adherence of participants

to administration of the second dose remained very high, even for the higher doses. Until 24 October 2021, no vaccine-related SAEs, AESIs, or fatalities were reported for any dose in the Phase 1 study. Increases in frequency or severity were not observed for Grade 3 solicited AEs in the later clinical phases with larger sample sizes.

Risk to study participants will be mitigated in several ways:

- 1) A stagger will occur between the younger and older adults based on SRT review of Days 1 to 8 safety data (including Day 8 laboratory data) from 3 sentinels (Cohort 1).
- 2) Each sentinel will be called at Day 2 (at least 20 hours postvaccination) to monitor their safety postvaccination prior to vaccination of the next sentinel.
- 3) The SRT will review Days 1 to 8 safety data (including Day 8 laboratory data) from 3 sentinels in each dose cohort (Cohorts 1-5) prior to expansion in the same dose cohort.
- 4) The SRT will review Days 1 to 8 safety data (including Day 8 laboratory data) from 3 sentinels prior to escalation to the next higher dose cohort (Cohorts 1-3).
- 5) The SRT will review data from the entire dose cohort prior to escalation to the next higher dose cohort (Cohorts 4-5).
- 6) The SRT will continue to review all available safety data to determine study progression.
- 7) Study holding rules have been specifically predefined so that the study will be fittingly put on hold pending the review of all accumulated safety data by the SRT and to decide whether expansion of vaccination and escalation through the higher dosages may continue.

Participants will be monitored for 6 months after receiving study vaccine on Day 1. Safety monitoring, including physical examinations, clinical laboratory assessments, vital sign measurements, and AEs (solicited and unsolicited AEs, SAEs, MAAEs, and AESIs), will be performed throughout the study via outpatient site visits and participant eDiary completion. Due to the ongoing pandemic, safety follow-up visits may be completed via televisits, as permitted by country regulations. In-person visits should be maintained in the study unless

Protocol 217741 (CV2 SARS-COV2-002 BST) Amendment 2

13 Jun 2022

there is a public health emergency limiting access to study sites. During such an emergency or extenuating circumstance, televisits can be employed to keep personal access to subjects and ascertain their safety at a high level.

Refer to the IB for nonclinical data for the CV2CoV vaccine. Refer to Section 1.2 for risk-benefit considerations.

4 Participant Selection and Withdrawal Criteria

4.1 Selection of Study Participants

A total of up to approximately 210 healthy adult participants (approximately 90 younger adults [≥18 to <65 years of age] and approximately 120 older adults [≥65 years of age]) will be enrolled in the study. Participants will be assigned to study vaccine only if they meet all of the inclusion criteria and none of the exclusion criteria.

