booster vaccination	GMI from baseline of binding IgG against SARS-CoV-2 S protein and RBD at each collection time point (Days 8, 15, 29, 85, and 180)		

Note: Tertiary objectives and endpoints are included in the main protocol.

Diagnosis and Main Criteria for Inclusion and Exclusion: The study will enroll healthy adults (≥18 to <65 years of age for the younger adult group and ≥65 years of age for the older adult group) who have received at least 2 doses of Pfizer-BioNTech (Comirnaty®) or Moderna (Spikevax®) mRNA COVID-19 vaccine (with the last dose of vaccine received at least 6 months prior to Screening and has provided documentation of receiving the vaccination series) and is negative for SARS-CoV-2 infection (by RT-PCR test) at Screening. History of documented SARS-CoV-2 infection or COVID-19 within 6 months before Screening, previous participation in an investigational vaccine study with investigational vaccine administered within 6 months of study vaccination or close contact with anyone who had a confirmed SARS-CoV-2 infection within 14 days before study vaccination will exclude individuals from study participation.

Study Design: This Phase 1 study will evaluate the safety, reactogenicity, and immunogenicity of the CV2CoV vaccine in SARS-CoV-2 seropositive healthy adult participants. The study will be conducted in 5 sequential cohorts with dose escalation from 2 μg to 20 μg. A total of up to approximately 180 healthy adult participants will be enrolled, 30 per dose group. The 30 participants will be distributed between the younger (≥18 to <65 years old) and older (≥65 years old) age groups, with a minimum of 10 and a maximum of 20 participants in each age group. There will be 3 sentinel participants in each age group within each dose group.

The study will be open-label. Participants in all cohorts will be screened for eligibility up to 14 days before enrollment. On Day 1, participants will receive study vaccine according to their cohort (dose group) and age group, and study visits will proceed according to the SOE. Participants will be sequentially enrolled to the dose level assigned to their cohort.

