Investigational Product, Dosage, and Route of Administration: Study vaccine will be administered on Day 1 as a single IM injection of 0.3 mL in the deltoid area, preferably in the nondominant arm.

The following IP will be used in the study:

	Investigational Product		
Description	CV2CoV ^a		
CCI	CCI		
CCI	WT CCI		
CCI	CCI		

a. Product reference: CV07050201.

Sample Size: Approximately 180 participants will be enrolled in the study, apportioned among cohorts, dose groups, and age groups according to the table below.

Cohort	Dose Group	Dose Level	Younger Adults ≥18 to <65 Years of Age	Older Adults ≥65 Years of Age	Total Dose Group Sample Size
1	1a	2 μg	$10 \le n \le 20$	$10 \le n \le 20$	30
	1b	4 μg	$10 \le n \le 20$	$10 \le n \le 20$	30
2	2	8 μg	$10 \le n \le 20$	$10 \le n \le 20$	30
3	3	12 μg	$10 \le n \le 20$	$10 \le n \le 20$	30
4	4	16 μg	$10 \le n \le 20$	$10 \le n \le 20$	30
5	5	20 μg	$10 \le n \le 20$	$10 \le n \le 20$	30

Statistical Methods: No formal significance testing will be performed. Analysis details, including any subgroup analysis, will be provided in the SAP.

For all safety endpoints, descriptive summary statistics will be provided for the Safety Set. Safety data listings will be provided, and graphical presentations will be considered as needed. In addition to the planned summary of SAEs throughout the study, any SAEs that are reported within 28 days of study vaccine administration will also be summarized.

For the immunogenicity endpoints, the GMTs of specific Ab with corresponding 95% CIs) at each time point and percentage of participants with seroresponse (≥4-fold rise from baseline) at Day 29 after the booster dose, and GMI from baseline of specific Ab with corresponding 95% CIs at each postbaseline time point over prevaccination baseline will be provided by dose group. The GMT, the GMI, and their 95% CI in all cohorts will be analyzed using an ANCOVA with treatment and age group as fixed factors and prevaccination baseline value as a covariable.

Version and Date of Protocol: Amendment 2; 13 Jun 2022

1 Introduction

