3.1 Study Design

This Phase 1 study will evaluate the safety, reactogenicity, and immunogenicity of the CV2CoV vaccine in SARS-CoV-2 seropositive healthy adult participants. The study will be conducted in 5 sequential cohorts with dose escalation from 2 μg to 20 μg. A total of up to approximately 180 healthy adult participants will be enrolled, 30 per dose group as indicated in Table 3-1. The 30 participants will be distributed between the younger (≥18 to <65 years old) and older (≥65 years old) age groups, with a minimum of 10 and a maximum of 20 participants in each age group. There will be 3 sentinel participants in each age group within each dose group. A study design schematic is provided in Figure 3-1.

Table 3-1 CV2CoV Study Cohorts, Dose Groups, and Dose Levels

Cohort	Dose Group	Dose Level	Younger Adults ≥18 to <65 Years of Age	Older Adults ≥65 Years of Age	Total Dose Group Sample Size
1	1a	2 μg	$10 \le n \le 20$	$10 \le n \le 20$	30
	1b	4 μg	$10 \le n \le 20$	$10 \le n \le 20$	30
2	2	8 μg	$10 \le n \le 20$	$10 \le n \le 20$	30
3	3	12 μg	$10 \le n \le 20$	$10 \le n \le 20$	30
4	4	16 µg	$10 \le n \le 20$	$10 \le n \le 20$	30
5	5	20 μg	$10 \le n \le 20$	$10 \le n \le 20$	30

Note: The first 3 participants enrolled in each age group within each dose group will be sentinel participants.

The screening period will be up to 14 days, study vaccine administration will occur on Day 1, and participants will have approximately 180 days (6 months) of follow-up after study vaccine administration. Study assessments will be performed in an outpatient setting at qualified study sites.

The study will be open-label. Participants in all cohorts will be screened for eligibility up to 14 days before enrollment. Participants will receive study vaccine according to their cohort (Table 3-1), dose group, and age group; and study visits will proceed according to the SOE (Table 13-1). Participants will be sequentially enrolled to the dose level assigned to their cohort.

Enrollment in each dose cohorts and the progression from vaccination in younger to older adult participants will be staggered based on SRT data review will progress as described in Section 7.8. Holding rules for dosing are described in Section 5.9.

[figure not shown]

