5.9 Study Holding Rules

The study holding rules in Table 5-2 will be applied independently to each dose group.

Table 5-2 Study Holding Rules

Study Holding Rule	Study Holding Rule Description	Number of Participants Needed to Trigger a Study Hold
1a	Death or any life-threatening SAE regardless of causality	≥1
1b	Any non-life-threatening SAE that cannot be reasonably attributed to a cause other than vaccination as per investigator or Sponsor assessment	≥1
1c	Any withdrawal from the study (by investigator or participant request) following a Grade 3 AE	≥1
1d	Any local or general solicited AE leading to hospitalization OR necrosis at the injection site; each with an event onset within the 7-day postvaccination period (Days 1 to 7)	≥1
1e	Severe cases of SARS-CoV-2 infection	≥2
1f	Any same or similar Grade 3 related unsolicited events, including but not limited to the identical MedDRA high-level term	≥2
1g	Same Grade 3 solicited local or systemic AE in an investigational group	>3
1h	Same Grade 3 or above abnormality in prespecified hematological or biochemical laboratory parameters with an event onset by Day 8 (± 1 day) postvaccination, except nonclinically significant lymphopenia	≥3
2a	Any Grade 3 solicited events in an investigational group, with an event onset within the 7-day postvaccination period (Days 1 to 7)	2 out of 3 first exposed participants 3 out of 5 first exposed participants 7 out of 16 first exposed participants 9 out of 22 first exposed participants 11 out of 28 first exposed participants 12 out of 30 first exposed participants (combined younger and older adult age groups)
2b	Any Grade 3 unsolicited AE , that can be reasonably attributed to the vaccination as per Investigator or Sponsor assessment, with an event onset within the 7-day (Days 1 to 7) postvaccination period	2 out of 15 first exposed participants 3 out of 30 first exposed participants (combined younger and older adult age groups)

Study holding rules 1a through 1d will be assessed by the investigators on a continuous basis. Study holding rules will lead to a halting of the entire study, with the exception of study

holding rule 1c, which will lead to halting of the concerned cohort and the next cohorts with higher doses.

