7.2 Sample Size Determination

The sample size is based on clinical considerations to inform dose regimen decisions for continued clinical development.

Approximately 180 participants will be enrolled in this Phase 1 study, with 6 dose-level cohorts each comprising 2 age groups. With 30 participants in each cohort, there is a 78.5% probability to observe at least 1 AE if the incidence rate is 5% and a 95.8% probability to observe at least 1 AE if the incidence rate is 10%. With 30 participants in each cohort, a 10% unevaluable rate for immunogenicity results, and a standard deviation of 0.45 for log₁₀-transformed increase from Day 1, the ratio of the upper limit of a 2-sided 95% CI and the point estimate of GMI is 1.5.

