4.1. Sample Size

The sample size is based on clinical considerations to inform dose regimen decisions for continued clinical development. Approximately 180 participants will be enrolled in this Phase 1 study, with 6 dose-level cohorts each comprising 2 age groups. With 30 participants in each cohort, there is a 78.5% probability to observe at least 1 AE if the incidence rate is 5% and a 95.8% probability to observe at least 1 AE if the incidence rate is 10%. With 30 participants in each cohort, a 10% unevaluable rate for immunogenicity results, and a standard deviation of 0.45 for log10-transformed increase from Day 1, the ratio of the upper limit of a 2-sided 95% CI and the point estimate of Geometric Mean Increase (GMI) is 1.5.

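### Protocol Section 4.1 plans about 210 participants (90 younger, 120 older), while the rest of the protocol and the SAP plan about 180, with 30 per dose group

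*Protocol*

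**What the plan says.** Protocol Section 4.1 (Selection of Study Participants) gives the enrolment target as "A total of up to approximately 210 healthy adult participants", split into approximately 90 adults under 65 and approximately 120 aged 65 or over.

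The other places that state the size of the study agree with one another and differ from Section 4.1:

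- **Synopsis, Study Design:** "A total of up to approximately 180 healthy adult participants will be enrolled, 30 per dose group". Protocol Section 3.1 and SAP Section 3.1 give the same total and dose group size.
- **Synopsis, Sample Size:** "Approximately 180 participants will be enrolled in the study, apportioned among cohorts, dose groups, and age groups according to the table below". That table, Table 3-1 and SAP Table 3.1-1 each show six dose groups of 30.
- **Protocol Section 3.1, age split within a dose group:** "with a minimum of 10 and a maximum of 20 participants in each age group".
- **Protocol Section 7.2:** "Approximately 180 participants will be enrolled in this Phase 1 study, with 6 dose-level cohorts each comprising 2 age groups". SAP Section 4.1 repeats this.

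The safety monitoring material is also set out for groups of 30. In Table 5-2 the last threshold of rule 2a is "12 out of 30 first exposed participants" and that of rule 2b is "3 out of 30 first exposed participants", both with the age groups combined. The scenarios in Table 13-2 use 30 participants at every dose.

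**The concern.** The protocol gives two ceilings for the number of people exposed in a first-time-in-human study, and two incompatible age distributions. Section 4.1 is the enrolment statement that stands directly before the inclusion and exclusion criteria, so it is a natural place for a site or ethics committee to look.

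The Amendment 2 summary of changes is not itself the error. It shows only that 210 is the older figure, and it lists Section 3.1, not Section 4.1, for the reduction. The sentence in Section 4.1 is operative text of the current protocol.

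The age limits alone would not reveal the problem. The per-group numbers implied by Section 4.1 satisfy the limits for each age group and break only the dose group total. If enrolment followed Section 4.1, each dose group would run past the size for which the detection probabilities were stated and past the last thresholds of rules 2a and 2b.

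**Working it through.** **Inputs.** From Section 4.1: 210 in total, 90 younger, 120 older. From Table 3-1: six dose groups of 30, with 10 to 20 per age group. From Section 7.2: AE incidences of 5% and 10%, 10% unevaluable for immunogenicity, and a standard deviation of 0.45 on the log10 scale.

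**The plan's own figures at 30 per group.**

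- Total: 6 × 30 = 180, as stated.
- Probability of at least one AE, 1 − (1 − p)^n: 1 − 0.95^30 = 0.785 and 1 − 0.90^30 = 0.958. Both match the stated 78.5% and 95.8%.
- Ratio of the upper 95% limit to the geometric mean increase (GMI), 10^(t × 0.45/√n), with 0.9 × 30 = 27 evaluable and t = 2.056 on 26 degrees of freedom: 1.507. This matches the stated 1.5.

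**Section 4.1.**

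- 90 + 120 = 210, so the sentence agrees with itself.
- Spread evenly over six dose groups: 90/6 = 15 younger and 120/6 = 20 older, 35 in all. The figure 35 is not printed in Section 4.1; it comes from this division.
- Excess: 210 − 180 = 30 participants; 210/180 = 1.167, or 17%.

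**Does the age split fit within 180?** The limits of 10 to 20 in six dose groups allow 6 × 10 = 60 to 6 × 20 = 120 in each age group. With 120 older, 180 − 120 = 60 younger. With 90 younger, 180 − 90 = 90 older. The pair 90 and 120 cannot occur. Per dose group, 15 and 20 each lie within 10 to 20; only their sum of 35 breaks the total of 30.

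**Which size do the stated operating figures belong to?**

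| Quantity | Stated | n = 30 | n = 35 |
|---|---|---|---|
| P(at least 1 AE), 5% incidence | 78.5% | 78.5% | 83.4% |
| P(at least 1 AE), 10% incidence | 95.8% | 95.8% | 97.5% |
| GMI ratio | 1.5 | 1.51 (27 evaluable) | 1.46 (31 evaluable) |

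For n = 35 the evaluable number is 0.9 × 35 = 31.5, rounded down to 31, with t = 2.042. The detection probabilities identify 30. The GMI ratio does not separate the two sizes, because both values round to 1.5.

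**Holding rules.** At 35 per group, (35 − 30) × 6 = 30 participants, or 30/210 = 14%, would lie beyond the last threshold of rules 2a and 2b.

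**The case against.** The strongest reply is that this is one sentence left unchanged in an amendment. Every passage that defines the design or justifies its size says 180. Section 4.1 prints no number per dose group, and the only group sizes in the documents are those in Table 3-1. Enrolment is tracked by interactive response technology (Section 5.1). No analysis set, model or endpoint uses 210, and the Section 7.2 figures need no change. Larger groups would improve AE detection, so the values at 35 show no harm. Rules 1a to 1h are counts without a denominator, and the Safety Review Team reviews all available safety data, so participants 31 to 35 would not go unmonitored. Finally, SAP Section 12 says the study was closed early, which may leave little for an amendment to change.

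Most of this stands as a limit on the consequences. The figures at 35 are conditional on sites following Section 4.1 instead of Table 3-1, and they measure the mismatch, not damage. The reply does not remove the contradiction. Sections 3.1 and 4.1 both hedge with the same phrase (up to approximately), which cannot absorb a gap of 30 or make 90 and 120 fit within 180. The documents do not state the caps in the enrolment system. Early closure changes where the correction goes, but planned enrolment still has to be reported as one number.

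**Conclusion.** The concern holds. Section 4.1 contradicts the rest of the protocol and the SAP on total enrolment (210 against 180, 30 participants or 17% more) and on the age split, which cannot be met within 180. The equivalent figure of 35 against 30 per dose group assumes an even spread over six groups.

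The design, the AE detection probabilities, the last thresholds of rules 2a and 2b and the Table 13-2 scenarios all rest on 30 per group, so 180 is the number the plan supports. This is an internal inconsistency in a figure the trial relies on. It should be corrected, but it does not bias or invalidate any planned analysis.

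**What to change.** In Section 4.1, state up to approximately 180 participants, 30 per dose group, with 60 to 120 in each age group and the two summing to 180. Changing the total alone is not enough, because the printed split would still add to 210.

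If no further amendment is planned because the study closed early, state in the CSR that planned enrolment was 180 and that Section 4.1 was not updated. SAP Section 13 (Changes in the Planned Analysis) is marked not applicable and does not settle the point.

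The cost is one sentence in either document. No participants, visits, samples or analyses change, and Section 7.2 and SAP Section 4.1 stand as they are.

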4.1.1 Inclusion Criteria

Each participant must meet all the following criteria to be enrolled in this study:

- 1. Must provide documented informed consent prior to any study procedures being performed.
- 2. Is capable of understanding and agrees to comply with planned study procedures and to be available for all study visits, including being willing and able to use electronic devices during the study.
- 3. Has received at least 2 doses of Pfizer-BioNTech (Comirnaty®) or Moderna (Spikevax®) mRNA COVID-19 vaccine, with the last dose of vaccine received at least 6 months prior to Screening and has provided documentation of receiving the vaccination series (eg, vaccination card).
- 4. Negative for SARS-CoV-2 infection by RT-PCR test at Screening.
- 5. Is a male or nonpregnant female 18 to <65 years of age (younger adult group) or ≥65 years of age (older adult group) at Screening.
- 6. Has a body mass index of 18 to 34.9 kg/m², inclusive, at Screening.
- 7. If the participant is a WOCBP, as described in Section 13.2, the participant agrees to practice true abstinence or use at least 1 highly effective form of contraception for at least 30 days prior to study vaccination up to 3 months after study vaccination.
- 8. Agrees to refrain from blood or plasma donation from Screening and throughout the end of the study.
- 9. Is healthy or medically stable as determined by medical history, clinical laboratory tests, vital sign measurements, and physical examination findings, as determined by investigator judgment.

